## 1.2 Synopsis

**Protocol Title:** A 26-Week, Phase 3, Open Label Study with a 12-Week, Placebo-Controlled, Randomized Withdrawal Period Followed by an Open Label Long Term Safety Extension to Evaluate the Safety and Efficacy of Tenapanor to Treat Hyperphosphatemia in End-Stage Renal Disease Patients on Hemodialysis and Peritoneal Dialysis

**Sponsor:** Ardelyx, Inc.

**Study Phase:** Phase 3

**Objectives:** The primary objectives of this study are:

- To evaluate the safety and tolerability of tenapanor for the treatment of hyperphosphatemia in End-Stage Renal Disease Patients on Hemodialysis (ESRD-HD) and on Peritoneal Dialysis (ESRD-PD) when administered twice daily for up to 52 weeks.
- To compare the phosphorus lowering effect between tenapanor and placebo based on the change in serum phosphorus (s-P) from the end of the 26-week treatment period to the end of the up to 12-week randomized withdrawal period or the endpoint visit for this period in the responder population (efficacy analysis set).

The secondary objectives of this study are:

- To compare the phosphorus lowering effect between tenapanor and placebo based on the change in serum phosphorus (s-P) from the end of the 26-week treatment period to the end of the randomized withdrawal period or the endpoint visit for this period in the intent-to-treat (ITT) analysis set and at individual doses of tenapanor and placebo in both the efficacy and ITT analysis sets.
- To evaluate the effect of tenapanor on the change in serum phosphorus levels from baseline to the end of 26-week treatment period.
- To evaluate the effect of tenapanor on the number of patients reaching serum phosphorus goal levels defined as  $< 5.5$  mg/dL during the 26-week treatment period.
- To evaluate the effect of tenapanor on Calcium- Phosphorus Product (Ca x P) during all three study periods (26-week treatment period, randomized withdrawal period and safety extension period).
- To evaluate the effect of tenapanor on intact fibroblast growth factor 23 (iFGF23) and c-terminal FGF23 (cFGF23) levels during all three study periods (26-week treatment period, randomized withdrawal period and safety extension period).
- To evaluate the effect of tenapanor on the Kidney Disease Quality of Life (KDQoL) survey during all three study periods.

- To evaluate the effect of tenapanor on the Dialysis Symptom Index (DSI) survey during all three study periods (for English speakers only).
- To compare the long-term safety of tenapanor to the active control sevelamer carbonate.

The exploratory objectives of this study are:

- To collect and store plasma/serum for future exploratory research into serum/plasma biomarkers related to cardio-renal disease and/or bone-metabolism or that may influence the response (i.e. distribution, safety, tolerability, and efficacy) to tenapanor. (These data will not be part of the study report.)

**Number of Sites:** 70 to 95 clinical sites in the US

**Number of Patients:** Approximately 560 ESRD patients on hemo- or peritoneal dialysis.

**Study Design and Duration of Treatment:** The study consists of a screening visit, a phosphate binder-free wash-out period of up to four weeks, a 26-week treatment period, an up to 12-week placebo-controlled, randomized withdrawal period, during which patients are randomized 1:1 to remain on the tenapanor dose they are taking at the end of the 26-week treatment or receive placebo, followed by an open label safety extension period for a total treatment period of up to 52 weeks. An active control group, for safety analysis, will receive sevelamer carbonate, open label, for the entire 52-week study period (see [Section 2.3](#)).

The screening visit (Visit 1) and all other visits in the study must be scheduled after a short dialysis interval (only for HD patients; e.g., Wednesday or Friday for patients on a MWF schedule and Thursday or Saturday for patients on a TThS schedule). Body weight, vital signs and blood collections for laboratory assessments **must** be performed pre-dialysis. All other assessments may be performed pre-, during, or post-dialysis but should be performed at the same time at each visit. For PD patients, visits should be performed on the same day each week, if possible.

Serum phosphorus measured at the screening visit must be  $\geq 4.0$  and  $\leq 8.0$  mg/dL for patients to be eligible to enter the wash-out period.

The wash-out period will begin immediately after the screening visit. Serum phosphorus will be measured weekly (pre-dialysis after a short interval for HD patients) during the wash-out period to determine if the patient meets inclusion criteria for enrollment into the study.

The study visits during the wash-out period for HD patients should be scheduled after the first short interval in the week to ensure data are available before a possible randomization, which could then take place after the second short interval in the week. Otherwise the randomization

visit will be scheduled the following week after the first short dialysis interval; therefore, the total length of time off phosphate binder treatment may be up to 4 weeks.

Patients who meet all inclusion/exclusion criteria will be randomized centrally 3:1 to either receive tenapanor at a dose of 30 mg bid or sevelamer carbonate based on package insert instructions (standard of care) after Visits 2, 3 or 4 (after 1, 2, or 3 weeks of wash-out) if they have a s-P level of at least 6.0 mg/dL and not more than 10.0 mg/dL and have an increase in s-P of at least 1.5 mg/dL versus pre wash-out (Visit 1, Screening Visit).

Patients randomized into the tenapanor group will receive tenapanor at a dose of 30 mg bid. Tenapanor will be taken twice daily; just prior to breakfast and dinner. Patients on HD should **not** take tenapanor at the meal immediately preceding dialysis; in this case, patients will take tenapanor prior to the next meal after dialysis. Those randomized into the active control group will take sevelamer carbonate based on standard of care using the package insert for guidance for the entire 52-week study period. Patients who are on active control will **not** have Visits 14, 16 and 18.

Investigators may decrease or increase the dose of tenapanor based on s-P levels and/or GI tolerability in 10 mg increments to a minimum of 10 mg bid or a maximum of 30 mg bid from enrollment until Day 183 (Visit 13). The dose of sevelamer carbonate may be adjusted based on standard of care for the entire 52-week study period.

During the 26-week treatment period and the safety extension period, patients on tenapanor with a s-P  $\geq 10$  mg/dL at any time after Week 2 of treatment or patients with a s-P  $\geq 9$  mg/dL for two consecutive visits after Week 2 will be discontinued and all visit procedures for Visit 23 will be completed, if possible. Patients in the active control group, receiving sevelamer carbonate do not have specific discontinuation criteria; they will be treated based on standard of care using the package insert for guidance.

At the end of the 26-week treatment period, patients in the tenapanor group only will be randomized 1:1 to either remain on the tenapanor dose they are taking on Day 183 (Visit 13) or receive placebo for up to an additional 12 weeks (randomized withdrawal period). During the randomized withdrawal period, patients with a s-P  $\geq 9$  mg/dL will be discontinued and all visit procedures for Visit 23 will be completed, if possible. Patients who discontinue from the randomized withdrawal period with s-P  $\geq 9$  mg/dL will be offered the opportunity to enter the safety extension period. In addition, patients who randomize into the

tenapanor group and complete the randomized withdrawal period are eligible to enroll in the open label safety extension period for an additional 14 weeks. Patients who enroll into the open label extension period will receive tenapanor.

Laboratory efficacy endpoints will be assessed at designated visits throughout the study; s-P will be measured at every visit.

Safety assessments will be performed during the study and will include physical examinations, vital signs (blood pressure and pulse), body weights, clinical laboratory evaluations, 12-lead electrocardiograms (ECGs), and adverse event (AE) monitoring

**Planned Sample Size:**

Approximately 560 male and female patients with end stage renal disease (ESRD) on chronic maintenance hemodialysis (HD) 3 times a week for a minimum of 3 months or chronic maintenance peritoneal dialysis (PD) for a minimum of 6 months are eligible to participate. Patients will be randomized 3:1 to receive either tenapanor or active control.

**Patient Selection Criteria:**

**Inclusion criteria:**

1. Signed and dated informed consent prior to any study specific procedures.
2. Males or females  $\geq$  18 years of age.
3. Females must be non-pregnant, non-lactating and fulfilling one of the following:
  - a. Post-menopausal defined as amenorrhea for at least 12 months following cessation of all exogenous hormonal treatments and with follicle stimulating hormone (FSH) levels in the laboratory defined post-menopausal range.
  - b. Documentation of irreversible surgical sterilization by hysterectomy, bilateral oophorectomy or bilateral salpingectomy but not tubal ligation.
  - c. Use of acceptable contraceptive method: IUD with spermicide, a female condom with spermicide, contraceptive sponge with spermicide, an intravaginal system (e.g., NuvaRing®), a diaphragm with spermicide, a cervical cap with spermicide, or oral, implantable, transdermal, or injectable contraceptives, sexual abstinence, or a sterile sexual partner.
4. Males must agree to avoid fathering a child (or donating sperm), and therefore be either sterile (documented) or agree to use, from the time of enrollment until 45 days after end of study, one of the following approved methods of contraception: a male condom with

spermicide, a sterile sexual partner, use of an IUD with spermicide by female sexual partner, a female condom with spermicide, contraceptive sponge with spermicide, an intravaginal system (e.g., NuvaRing®), a diaphragm with spermicide, a cervical cap with spermicide, or oral, implantable, transdermal, or injectable contraceptives.

5. Chronic maintenance hemodialysis 3x/week for at least 3 months or chronic maintenance peritoneal dialysis (PD) for a minimum of 6 months. If modality of dialysis has changed, patient must meet one of the two dialysis criteria above and been on the new modality of dialysis for a minimum of one month.
6. Stable vascular access as assessed by Investigator, if on HD.
7.  $Kt/V \geq 1.2$  at most recent measurement prior to screening.
8. Prescribed and taking at least 3 doses of phosphate binder per day. The prescribed dose should have been unchanged during the last 3 weeks prior to screening.
9. Serum phosphorus levels must be between 4.0 and 8.0 mg/dL (inclusive) at screening, analyzed at the central laboratory used in the study.
10. Intentionally left blank.
11. For enrollment in the study, patients must have serum phosphorus levels of at least 6.0 mg/dL but not more than 10.0 mg/dL and have had an increase of at least 1.5 mg/dL versus pre wash-out value after 1, 2 or 3 weeks wash-out of phosphate binders.
12. Able to understand and comply with the protocol.

**Exclusion criteria:**

1. Severe hyperphosphatemia defined as serum phosphorus greater than 10.0 mg/dL on phosphate-binders at any time point during clinical monitoring for the 3 preceding months before the screening visit.
2. Serum/plasma parathyroid hormone >1200 pg/mL. The most recent value from patients' medical records should be used.
3. Clinical signs of hypovolemia at enrollment as judged by the investigator.
4. History of inflammatory bowel disease (IBD) or diarrhea predominant irritable bowel syndrome (IBS-D).
5. Scheduled for living donor kidney transplant, plans to change to a different method of dialysis, home HD or plans to relocate to another center during the study period.

6. Any evidence of or treatment of malignancy within one year, excluding non- melanomatous malignancies of the skin.
7. Positive serology (hepatitis C or B infection, or human immunodeficiency virus) **with** evidence of significant hepatic impairment or WBC elevation according to the Investigator.
8. History of alcohol abuse, illicit drug use, significant mental illness, or any history of drug abuse or addiction within 12 months of study enrollment.
9. Life expectancy <12 months.
10. Use of an investigational agent within 30 days prior to Screening.
11. Previous randomization into this study.
12. Previous exposure to tenapanor.
13. Involvement in the planning and/or conduct of the study (applies to both Ardelyx/CRO staff and/or staff at the study site).
14. If, in the opinion of the Investigator, the patient is unable or unwilling to fulfill the requirements of the protocol or has a condition which would render the results uninterpretable.

**Study Drug:** Tenapanor 10 mg tablets and matched placebo

**Active Control:** Sevelamer carbonate tablets (800 mg)

**Dose and Route of Administration:** Tenapanor will be administered PO at the following dose levels:

- 26-week treatment period: Titration scheme (from Randomization (Visit 5) to Day 183 (Visit 13): starting dose 30 mg bid, dosing may be down-titrated or up-titrated to a maximum of 30 mg bid in a step-wise fashion based on serum phosphorus levels and/or GI tolerability. Down-titration can go from 30 mg bid to 20 mg bid to 10 mg bid. Dose escalation can go in 10 mg bid increments to a maximum dose of 30 mg bid.
- Randomized withdrawal period: Fixed dose based on last dose from 26-week treatment period.
- Safety extension period: Starting dose is the same dose from the end of the 26-week treatment period. Titration is allowed as described for the 26-week treatment period.

Sevelamer carbonate (active control) will be administered PO based on standard of care during the entire 52-week study period.

Placebo will be administered PO during the randomized withdrawal period only. During this period, patients will be randomized 1:1 to receive either placebo or tenapanor. The placebo group will receive the

same number of tablets as the last dose of tenapanor they received during the 26-week treatment period. Patients from the active control group will not enter the randomized withdrawal period; they will continue to receive sevelamer carbonate per standard of care for all 52 weeks.

A detailed description of the dose adjustment procedures can be found in [Section 6.1.3](#).

**Statistical  
Analyses:**

**Analysis sets:**

**Safety Analysis Set (at each study period):**

All patients who receive at least one dose of study drug (tenapanor or placebo) or active control for the individual study period. The safety analysis set will be used for the analysis of all safety variables.

**Intent to Treat (ITT) Analysis Set (at each study period):**

All patients who meet the study entry inclusion/exclusion criteria, receive at least one dose of tenapanor or placebo, and have at least one post-treatment serum phosphorus for the individual study period. The ITT analysis set will be used for the analysis of all efficacy variables.

**Efficacy Analysis Set (12-week randomized withdrawal period):**

All patients who meet the study entry inclusion and exclusion criteria, receive at least one dose of tenapanor during the 26-week treatment period, complete the 26-week treatment period, and achieve at least a 1.2 mg/dL reduction in serum phosphorus from baseline to the end of the 26-week treatment. The efficacy analysis set will be used for the primary efficacy analysis.

**Per-Protocol (PP) Analysis Set (12-week randomized withdrawal period):**

All patients in the ITT analysis set who completed the 12-week randomized withdrawal period as planned with no major protocol deviations that impact the primary efficacy variable. The PP analysis set will be used for sensitivity analyses to support the primary and key secondary efficacy analyses.

**Efficacy analyses:**

All efficacy variables will be summarized by treatment (including dose, if applicable) group, using descriptive statistics. All continuous efficacy variables (s-P, Ca x P, iFGF23, cFGF23, KDQoL and DSI) will be analyzed using an analysis of covariance (ANCOVA) model with terms for pooled investigator site, treatment (including dose, if

applicable), and baseline as the covariable. The change from baseline will be the dependent variable. The least squares means (LSmeans) will be presented for the change from baseline values for each treatment group (including dose, if applicable) with the 95% confidence interval (CI).

The primary efficacy variable will be the change in serum phosphorus from the end of the 26-week treatment period to the end of the 12-week randomized withdrawal period or the endpoint visit for this period. The primary efficacy analysis will be based on the difference between the tenapanor treatment and placebo treatment group in the responder population (efficacy analysis set). Endpoint for this analysis is defined as the last serum phosphorus lab value assessment during and up to the end of the 12-week randomized withdrawal period.

Secondary analyses are described in [Section 9](#) and are detailed in the statistical analysis plan (SAP).

**Safety analyses:**

Adverse events will be coded using the Medical Dictionary for Regulatory Activities (MedDRA) and will be summarized by system organ class, preferred term, and treatment (including dose, if applicable) group. For a change in stool form and/or frequency to be considered an adverse event, the criteria detailed in [Section 7.3.6.1](#) must be followed. These summaries will be provided for each study period separately.

Actual values and change from baseline values for clinical laboratory tests, vital signs, body weights, and ECGs will be summarized by each treatment (including dose, if applicable) group for each visit collected during the study. The number and percentage of patients in each physical examination category will be presented for each visit by treatment (including dose, if applicable) group. These summaries will be provided for each study period separately.

### 1.3 Schedule of Events

Study Day	Screening	Washout a			26-Week Treatment Period								
	-21	-14 ±2	-7 ±2	-1 ±2	1	8 ±5	15 ±5	29 ±5	57 ±7	85 ±7	120 ±7	155 ±7	183 ±7
Visit	V1	V2	V3	V4 a	V5 a	V6	V7	V8	V9	V10	V11	V12	V13
Informed consent	X												
Inclusion/Exclusion	X	X	X	X	X								
Demographics	X												
Pre-dialysis Body Weight	X f				X					X			X
Kt/V e	X												
KDQoL/DSF g	X									X			X
Med/Surgical Hx	X	X	X	X	X								
Physical Exam	X				X								X
Vital signs a	X	X	X	X	X	X	X	X	X	X	X	X	X
ECG evaluation	X				X					X			X
Clinical laboratory tests b	X				X					X			X
FSH test c	X												
Pregnancy test c (serum)	X				X					X			X
HIV, hepatitis B and C tests	X												
Start wash-out of phosphate binders	X												
Randomization #1 k					X								
Drug dispense					X	X		X	X	X	X	X	
Drug return						X		X	X	X	X	X	X
Drug accountability l						X		X	X	X	X	X	X
s-Phosphorus i	X	X	X	X	X	X	X	X	X	X	X	X	X
Ca x P, FGF23	X				X					X			X
Exploratory biomarkers	X				X					X			X
AE assessment d	X	X	X	X	X	X	X	X	X	X	X	X	X
Prior/ConMeds	X	X	X	X	X	X	X	X	X	X	X	X	X

Study Day	Randomized Withdrawal Period e							Safety Extension Period			
	183 +7	197 +7	211 +7	225 +7	239 +7	253 +7	267 +7	281 +7	309 +7	337 +7	365 +7
Visit	V13	V14 m	V15	V16 m	V17	V18 m	V19	V20	V21	V22	V23/ EOT
Pre-dialysis Body Weight							X			X	X
KDQoL/DSI f							X				X
Physical Exam							X				X
Vital signs a		X	X	X	X	X	X	X	X	X	X
ECG evaluation							X				X
Clinical laboratory tests b							X				X
Pregnancy test c (serum)							X				X
Randomization #2 k	X										
Drug dispense	X	X	X	X	X	X	X	X	X	X	
Drug return		X	X	X	X	X	X	X	X	X	X
Drug accountability		X	X	X	X	X	X	X	X	X	X
s-Phosphorus i		X	X	X	X	X	X	X	X	X	X
Ca x P, FGF23			X		X		X				X
Exploratory biomarkers			X		X		X				X
AE assessment d	X	X	X	X	X	X	X	X	X	X	X
Prior/ConMeds	X	X	X	X	X	X	X	X	X	X	X

- a Vital signs include blood pressure, pulse and must be performed pre-dialysis.
- b All blood collections are performed pre-dialysis.
- c FSH test and pregnancy test are performed on all females at Screening. After screening, pregnancy tests will only be performed on females of child-bearing potential.
- d AEs and SAEs will be collected from consenting to the end of study.
- e Kt/V should be the most recent historical value prior to screening.
- f Height will also be measured at the screening visit
- g In the randomized withdrawal period, patients in the tenapanor group only are randomized 1:1 to either stay on current treatment of tenapanor or receive a matched placebo; based on withdrawal criteria, patients may enter the safety assessment period at any visit.
- h If the laboratory evaluations from the wash-out period deem the patient ineligible for the study, the site must inform the patient and tell them to take their phosphate binders.
- i s-Phosphorus sample collected at visits when safety labs are not collected.
- j KDQoL (KDQoL™-36), Kidney Disease and Quality of Life survey. DSI, Dialysis Symptom Index survey is for English speakers only and is not validated in other languages.
- k Randomization #1 is 3:1, tenapanor: active control. Randomization #2 is 1:1 from the tenapanor group only to tenapanor: placebo. Patients in the active control group will receive sevelamer carbonate for the entire 52-week study period.
- l Drug accountability will be performed for both tenapanor and the active control.
- m Visits 14, 16 and 18 are not done for subjects randomized into the active control group.
- n Patients should be randomized by the week after meeting s-P washout criteria; total period off binder must not be greater than 4 weeks.

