#### 6.1.4 Method of Assigning Patients to Treatment Groups

The CRO or designated statistician will prepare the randomization scheme in accordance with its standard operating procedures (SOPs) and the randomization plan, which reflect Good Clinical Practice (GCP) standards.

After obtaining informed consent, patients will be allocated sequential enrollment numbers in their order of completing Screening assessments.

Patients will be randomized after the washout period 3:1 to receive tenapanor or the active control, sevelamer carbonate. Patients in the tenapanor group will be randomized a second time at the end of the 26-week treatment period to enter into the randomized withdrawal period (Visit 13) to either remain on their current dose of tenapanor or a matched placebo in a 1:1 ratio. Randomization codes will be assigned via an Interactive Response Technology (IRT).

The IRT will allocate the treatment and provide the randomization number for both the 26-week treatment period and the randomized withdrawal period. The IRT will provide the appropriate bottle ID chosen from those bottle IDs available at the study site for tenapanor and placebo only. The randomization is carried out at study level and the assigned randomization numbers and the associated bottle IDs will not be sequential within a study site. The active control will not have unique bottle ID #s.

If a patient withdraws from participation in the study, then his/her enrollment/ randomization code cannot be reused.

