### **9.2 Determination of Sample Size**

Approximately five hundred sixty (560) male and female patients with end stage renal disease (ESRD) on chronic maintenance hemodialysis (HD) 3 times a week for a minimum of 3 months or peritoneal dialysis (PD) for a minimum of 6 months will be enrolled in this study. Patients will be randomized in a 3:1 ratio to receive either tenapanor (~420 patients) or active control (~140 patients). Those patients in the tenapanor group will be randomized at the end of the 26-week treatment period to enter into the randomized withdrawal period to either remain on their current dose of tenapanor or placebo in a 1:1 ratio.

For the primary efficacy analysis, a sample size of 146 patients (73 patients/group) in the 12-week randomized withdrawal period is expected to provide more than 95% power to detect a difference between tenapanor and placebo treatment in the change in serum phosphorus from the end of the 26-week treatment period to the end of the 12-week randomized withdrawal period or the endpoint visit for this period, between the tenapanor treatment and placebo. This calculation is based on a two-sample t-test with a two-sided significance level of  $\alpha=0.05$ , an assumed treatment difference of 1.0 mg/dL and a common standard deviation of 1.6 mg/dL. This sample size (560) allows for a 30% dropout rate, meaning 30% of patients will not complete the 26-week treatment period. This sample size also assumes at least 50% of patients in the tenapanor group will be considered responders in the 26-week treatment period, i.e., patients who achieves at least a 1.2 mg/dL reduction from baseline to the end of the 26-week treatment period.

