#### 9.4.3 Primary Efficacy Analysis

The primary efficacy variable is the change in s-P from the end of the 26-week treatment period (Visit 13) to the end of the 12-week randomized withdrawal period (Visit 19) or the endpoint visit for this period. An endpoint visit is defined as the last visit with an s-P assessment during the randomized withdrawal period. The primary interest of this study is the difference between the tenapanor treatment and placebo treatment group in the mean change (w.r.t. the primary efficacy variable) in the responder population (the efficacy analysis set). A responder is a patient that had a serum phosphorus decrease of  $\geq 1.2$  mg/dL from enrollment (Day 1) to the end of the 26-week treatment period (Visit 13). The primary efficacy variable will be analyzed using an ANCOVA model. The model includes fixed effects for treatment, pooled investigator site, and the baseline s-P value as a continuous covariate. The baseline for this analysis is defined as the s-P value at the end of 26-week treatment period. Within the framework of this model, the difference between the tenapanor treatment and placebo treatment in the mean change from the end of the 26-week treatment period to the end of the 12-week randomized withdrawal period (or the endpoint visit for this period) will be estimated. The corresponding two-sided 95% CI and the p-value for the treatment difference will also be presented. Statistical significance will be declared if the estimated difference between the tenapanor treatment and placebo treatment in the mean change is negative (i.e.,  $< 0$ ) and the corresponding two-sided p-value is  $\leq 0.05$ .

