#### 9.4.4 Secondary Efficacy Analyses

##### 9.4.4.1 Key Secondary Efficacy Analyses

The analysis method described for the primary efficacy variable in [Section 9.4.3](#) will be performed as follows:

- in the ITT analysis set
- to compare the individual doses of tenapanor and placebo in the ITT analysis set – from high dose to low dose
- to compare the individual doses of tenapanor and placebo in the efficacy analysis set – from high dose to low dose

A sequential testing procedure will be used to control the family-wise type I error rate associated with the key secondary efficacy analyses. Specifically, the primary efficacy analysis will be performed at the 5% significance level. If statistical significance is declared for this analysis, then the first key secondary efficacy analysis listed in this section will be performed at the 5% level. If statistical significance is declared for this analysis, then the next key secondary efficacy analysis will be performed at the 5% level. This procedure continues until one of the key secondary efficacy analysis in the list results in a p-value >5%. Statistical significance will be declared for secondary efficacy analyses up to this point in the list.

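### Visit 13 tenapanor dose is left out of the primary ANCOVA and the MMRM, and the protocol names no stratification factor for Randomization #2; adding dose costs almost nothing and may sharpen the estimate slightly

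*Combined protocol and SAP*

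**What the plan says.** Footnote k of the Schedule of Events (section 1.3) gives the second allocation as "Randomization #2 is 1:1 from the tenapanor group only to tenapanor: placebo". Section 6.1.4 says that the IRT allocates treatment for both randomizations, that "The randomization is carried out at study level", and that the scheme is prepared under a separate randomization plan. No section names a stratification factor.

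For the primary analysis, section 9.4.3 states: "The model includes fixed effects for treatment, pooled investigator site, and the baseline s-P value as a continuous covariate". Baseline here is the Visit 13 phosphorus value. The MMRM in section 9.4.5 uses the same terms plus visit and treatment-by-visit. Dose is in neither model.

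Dose has a clear place elsewhere in the plan. Sections 4.1 and 6.1.3 let investigators titrate on phosphorus and GI tolerability up to Visit 13. The synopsis and section 4.1.1 then hold the dose for the withdrawal period and give placebo patients the same tablet count. Section 9.4.4.1 includes a step "to compare the individual doses of tenapanor and placebo in the efficacy analysis set", a matching step in the ITT set, both from high to low dose, and a fixed testing sequence. Three doses in two sets make six dose tests.

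**The concern.** A variable that is fixed before randomization, recorded for every patient, driven partly by the outcome measure, and important enough to define six tests in the error-controlled sequence would normally appear in the primary model. Dose reflects 26 weeks of response and tolerability. Two patients with equal Visit 13 phosphorus but different doses may behave differently once treatment is withdrawn. If dose is prognostic in that way, leaving it out keeps explainable variance in the residual and lets chance dose imbalance between arms add noise to the primary contrast.

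The stake is precision only. The randomized comparison is valid with or without the term.

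**Working it through.** **The plan's own figure.** Section 9.2: "This calculation is based on a two-sample t-test with a two-sided significance level of" 0.05, with "an assumed treatment difference of 1.0 mg/dL and a common standard deviation of 1.6 mg/dL" and 73 patients per group, "is expected to provide more than 95% power to detect a difference between tenapanor and placebo treatment". The noncentral t distribution gives 96.3% and the normal approximation 96.5%, so the statement reproduces. The standard error is 1.6 × √(2/73) = 0.265 mg/dL.

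**Who is randomized and who is analysed.** Completers at Visit 13: 420 × 0.70 = 294. Responders in the primary analysis: 294 × 0.50 = 147, against 146 planned. Randomization #2 covers the 294, not just the 147.

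**Assumptions not in the documents.** A dose split of 60/25/15% at 30/20/10 mg bid, and a linear difference in mean change of b mg/dL per dose step.

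**Variance that a dose term could remove.** Scoring dose 2, 1, 0, the mean is 1.45 and the variance is 2.65 − 1.45² = 0.5475. The share of the planned variance is R² = 0.5475 b² / 1.6²:
- b = 0.25: 0.034/2.56 = 1.3%, so the SE falls by at most 1 − √(1 − 0.013) = 0.7%
- b = 0.50: 0.137/2.56 = 5.3%, at most 2.7%
- b = 0.75: 0.308/2.56 = 12.0%, at most 6.2%

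These are ceilings. They ignore the cost of estimating two coefficients and any overlap with Visit 13 phosphorus and site.

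**Simulated SE, dose term alone, no stratification.** Starting from 0.265, the SE is 0.265, 0.260 and 0.250 for the three slopes: reductions of about 0%, 1.9% (0.005/0.265) and 5.7% (0.015/0.265). If dose matters only in the placebo arm, the values are about 0.267, 0.265 and 0.263, which is essentially no gain.

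**Power with residual SD 1.6√(1 − R²), 73 per arm (noncentral t).** R² = 5%: 97.1%. R² = 10%: 97.7%. Both compare with 96.3%. In simulation at R² = 0, power is 96.3% without and 96.2% with the term, so the cost of a useless term is about 0.1 point.

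**Sensitivity to the split.** At 80/15/5% the score variance is 0.2875 and the three R² values become 0.7%, 2.8% and 6.3%, roughly half.

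**What stratification adds.**
- Without it, the between-arm difference in the 30 mg bid share among responders has SD √(2 × 0.6 × 0.4/73) = 0.081, and exceeds 10 points in about 22% of trials.
- Stratifying all 294 balances those randomized. Half of them are responders, so about half the variance remains: SD 0.081 × √0.5 = 0.057. The difference then exceeds 10 points in about 8% of trials.
- At 10 mg bid, about 44 are randomized and 22 are responders (assuming 50% response at each dose). A split of 2:1 or worse falls from 13.4% to 3.4%. Power against same-dose placebo rises only from 27.6% to 28.1%.

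**The case against.** The strongest case against is that covariate choice is a matter of judgement. A prespecified ANCOVA with site and baseline phosphorus is a proper analysis, power already exceeds 96%, and any figure for the gain rests on a dose split and slope that the documents do not supply. Visit 13 phosphorus may absorb part of the dose effect because dose is titrated on it. Six secondary dose tests do not show that the primary model needs dose either: within a single dose the term would be constant. All of this stands, and it limits the point to a low-cost refinement.

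Three stronger readings are tempting, and the documents support none of them.
- A reader might infer that Randomization #2 is unstratified or simple. Footnote k gives only a ratio, and the study-level remark in section 6.1.4 sits beside text on numbering within sites. The scheme is in a randomization plan that is not in the reviewed text, nor is the separate SAP, which governs under section 9.1. All that can be said is that no factor is named.
- A reader might infer that precision is certainly being lost. That holds only if dose predicts the outcome beyond the terms already in the model.
- A reader might infer that open-label knowledge of dose opens a route to selection. Allocation is by IRT and the withdrawal period is double-blind. Knowing the dose only means that it is available as a stratum.

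What the objection does not answer is that the covariate is valid, already recorded and nearly free.

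**Conclusion.** The point holds as a minor improvement, not as an error. Visit 13 dose is a baseline variable for both arms and is missing from the written ANCOVA and MMRM, and the protocol is silent on stratification of Randomization #2. Type I error, unbiasedness and the claim of more than 95% power are unaffected.

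Under the assumed 60/25/15% split and slopes of 0.25 to 0.75 mg/dL per step, the SE of the primary contrast falls by about 0 to 6%. Power rises by about 1 to 2 points at R² of 5 to 10%, and not at all at R² = 0. A more uneven split, overlap with Visit 13 phosphorus, or a dose effect confined to placebo would shrink this further. Most of the benefit comes from the model term. Stratification reduces dose imbalance among responders without removing it, and barely changes dose-level power.

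**What to change.** - In sections 9.4.3 and 9.4.5, and in the SAP, add Visit 13 tenapanor dose (three levels) as a prespecified fixed factor. For placebo patients this is the last tenapanor dose before Randomization #2.
- Because section 9.4.4.1 reuses the primary method, add a sentence that the factor drops out of any comparison made within one dose.
- In section 6.1.4, state the stratification factors of Randomization #2, or state that there are none. If the IRT can still change and the randomization plan does not already do so, stratify by Visit 13 dose. If it cannot change, the model term alone remains valid.

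The cost is 2 degrees of freedom out of about 140, one IRT setting if it is still open, and a negligible loss of precision if dose turns out not to be prognostic. No extra data or patients are needed. The model change should be fixed before unblinding.
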